The protocol was later amended and participants in Groups 1 and 2 were given the option to receive a third dose for 3 total doses. Nine (out of 17) participants elected to receive a third dose. There were no unsolicited Grade-3 or -4 AEs and no related serious adverse events (SAEs), AESIs, or deaths in either group after this third dose. Both local and systemic reactogenicity were similar between all 3 doses in participants who received 3 doses.

HVTN 137 Part B is evaluating the safety and immunogenicity of 100 mcg BG505 SOSIP.664 gp140 in combination with 3 TLR agonists, including 5 mcg 3M-052-AF + 500 mcg Alum, and Alum alone. As of April 17, 2022, enrollment is complete and 88 participants have been enrolled. Of these 88 participants, 20 have been randomized to the 3M-052-AF group. All 88 participants have received at least two doses and 63 have received the third dose. Given that the trial remains blinded across 4 treatment arms, interpretation of the blinded safety data from HVTN 137 Part B is challenging, but there have been no related SAEs, AESIs, deaths, or unplanned study pauses. No additional grade 3 local reactogenicity events have been observed.

Overall, the BG505 SOSIP.664 with 3M-052-AF was generally well tolerated, with no unsolicited Grade-3 or -4 AEs, no related SAEs, AESIs, or deaths, and no unplanned study pauses. Other than the persistent erythema in 1 of the HVTN 137 Part A Group 2 participants described above, all reactogenicity symptoms resolved within 14 days and generally within 7 days. For more detailed information, please see the IB.

HVTN 300 (NCT04915768): This study is a first-in-human, unblinded trial testing a 300-mcg dose of a CH505 TF chTrimer (a stabilized, chimeric SOSIP Env trimer) in combination with 5 mcg 3M-052-AF + 500 mcg Alum delivered via split injection into both the right and left deltoids. The planned schedule is 5 total vaccinations at months 0, 2, 4, 8, and 12. As of September 7, 2022, the study is ongoing and all 13 participants have received the first vaccination, 10 participants have received the second vaccination, 9 participants have received the fourth vaccination, and 6 participants have received the fifth vaccination. Five (5) participants have discontinued further vaccinations, 1 due to a panic attack after the first injection (this participant had a history of panic attacks before being part of the study), 3 due to reactogenicity events and 1 was lost to follow-up. Out of these 5, 2 terminated from the study early (panic attack and lost to follow-up) and 3 have remained in the study for follow-up.

All participants experienced at least some local reactogenicity during the trial, mostly mild to moderate. One (1) participant experienced severe pain/tenderness in both the right and left injection sites 3 days following the fourth vaccination, though it lasted only one day.

Nearly all participants reported some systemic reactogenicity during the course of the trial to date, mostly mild to moderate. For example, 11 of 13 participants experienced systemic reactogenicity after the first dose. Five (5) participants reported Grade 3 (severe) systemic reactogenicity during the trial through September 7, 2022. One (1) of those participants received a subsequent vaccination without any Grade 3 reactogenicity, one participant experienced an additional repeat Grade 3 systemic reactogenicity symptom after a subsequent vaccination, one participant has not yet received a subsequent vaccination, and two (2) participants declined further vaccinations after their first Grade 3 systemic reactogenicity event.

All Grade 3 events resolved within the 7-day reactogenicity period; the longest duration for severe reactogenicity was 2 days.

There have been no related SAEs, AESIs, or deaths as of September 7, 2022.

2.5 Rationale for evaluation of 3M-052-AF + Alum adjuvant

3M-052-AF contains 3M-052 and an emulsifier in an aqueous formulation. 3M-052 is a TLR7 and TLR8 agonist (TLR7/8 agonist) that induces production of cytokines in vitro from immune cells, such as dendritic cells, macrophages, and monocytes (25-28).

Nonclinical studies in guinea pigs, rats, rabbits, and rhesus macaques comparing the immunogenicity of the related SOSIP protein BG505 SOSIP.664 formulated with a diverse range of adjuvants have consistently shown that the protein adjuvanted with 3M-052-AF elicits neutralizing and binding Abs more quickly, to higher-peak magnitudes, and with greater durability than any of the other protein-adjuvant combinations tested (29).

In rhesus macaques among 8 adjuvants combined with an Env gp140 immunogen, the Alum/TLR7 was the most potent in assays characterizing both Ab and cellular responses. This hierarchy of potency was sustained throughout the longitudinal follow-up. The overall effect of the Alum/TLR combination was to boost Env binding Ab titers 3-to-10-fold compared to Alum alone (30).

The 3M-052-AF adjuvant is a TLR7/8 agonist added to vaccine antigens to generate strong Ab responses in several nonhuman primate (NHP) models, and is currently being evaluated in HVTN 137 and HVTN 300 clinical trials (see Section 2.4). Combining 3M-052-AF with Alum results in a synergistic increase in immune responses to vaccine antigens in preclinical models, including Ab titers, CD4+ T-cell responses, infiltrating monocytes and dendritic cells, and B-cell activation when compared to either Alum or 3M-052-AF alone (25). In NHPs immunized with SARS-CoV-2, the receptor binding domain (RBD) formulated with 3M-052-AF combined with Alum and increased Ab titers, RBD binding and effector Abs, Th1 biased CD4+ T cells, and protection from SARS-CoV-2 viral challenge when compared to Alum alone (31).

For additional information, see the IB.

2.6 Rationale for schedule

Previous trials of DNA vaccines for HIV-1 Env immunogens have used a 0-, 1-, 3-, and 6-month vaccination schedule, exactly as proposed in this study. Those regimens were well tolerated and immunogenic (14, 15). Specifically for ID delivery, both Ab and T-cell responses were induced (17, 18). In HVTN 098, the fourth vaccination boosted the magnitude of total Ab response for all treatment groups against gp140 antigens from clades A and B as compared to the magnitude

of total Ab response after the third dose (18). By including a boost of Trimer 4571 at month 6 in Group 3, we can assess whether additional doses of protein and DNA lead to enhanced immunogenicity compared to DNA alone in this study (Group 2) and previous studies. By maintaining a standard schedule, data will be directly comparable to previous DNA vaccine studies.

2.7 Rationale for evaluation of boost with trimeric protein

Trimer 4571 is a stabilized NLT derived from the BG505 isolate in a gp140 format, modified with a different set of mutations to prevent CD4-induced conformational triggering (32-34). In proof-of-concept preclinical studies in guinea pigs, Trimer 4571, adjuvanted with Alum, induced autologous nAbs to BG505.W6M.C2 after the second administration, which increased further after the third administration. Rhesus macaques immunized via IM injection with research-grade Trimer 4571 produced nAbs to BG505.W6M.C2.T332N (see the IB for more details on these BG505 variants).

2.8 Rationale for targeting the same draining lymph node with both DNA and protein trimer

Direct targeting of the draining lymph node with a multipronged immune stimulus consisting of both a DNA vaccine and an adjuvanted protein vaccine led to improved outcomes in a variety of several preclinical models (12, 35-37). The most directly relevant study is that of Felber et al in rhesus macaques (37). This study compared vaccination with monomeric HIV envelope administered via both DNA and an adjuvanted protein delivered into the same limb or into contralateral limbs. This method allowed for a direct comparison of 2 injections with the same regimen (protein and DNA) at the same time in the same limb versus spacing simultaneous injections into contralateral limbs. Vaccination targeting the same draining lymph nodes led to improvement in a variety of immune outcomes, including functional Ab responses (increased ADCC activity and improved FcRIIIa binding) and cellular responses (CD4+ and CD8+). The proposed mechanism involves simultaneous priming of both CD4+ T cells (mostly induced by DNA) and Env-specific B cells (mainly induced by the adjuvanted protein component) in the same lymph node when injections were given in the same limb.

Most importantly, vaccination targeting the same draining lymph nodes resulted in superior protection against the simian-human immunodeficiency virus (SHIV) challenge (see Figure 2-3).

[figure not shown]

Figure 2-3 Coadministration group shows significant protection from SHIV.CH505 infection. (A) Schematic representation of vaccine delivery of the 2 components (DNA and protein) in the 2 vaccination regimens, "coadministration" in the same anatomical sites and "separate administration" in contralateral sites. The coadministration group received DNA delivered via IM EP, followed immediately by IM injection of the adjuvanted protein. The separate administration group received the vaccine components in different anatomical sites, with DNA delivered by IM EP in the left site and protein IM in the right site. The same vaccine components and the same total vaccine dose were used for both regimens. (B) Vaccination schedule indicating the sequentially isolated CH505 immunogens used. Five weeks after the last vaccination, the animals were exposed weekly to repeated low-dose vaginal challenges using SHIV.CH505. (C) Kaplan-Meier curves show the viral acquisition rate after repeated low-dose SHIV.CH505 challenges of the 2 vaccine groups (n = 18 and n = 17, respectively) and of the control group (n = 20). The RMs were exposed to 15 weekly intravaginal challenges. Infection was defined by 2 consecutive positive plasma viral load (VL) measurements. No RMs were censored. P value, exact log-rank test (37).

In keeping with the well tolerated safety profile of simultaneous delivery of HIV immunogens via both DNA+ envelope protein administration strategies (38) (39), no AEs were noted with either strategy (separation versus targeting the same draining lymph node), including assessments via clinical chemistry, complete

blood counts (CBCs), body weight, temperature, and regular physical exams by veterinarians. Additionally, theoretical concerns regarding increased local reactogenicity are mitigated by the observation that the DNA vector does not disperse from the site of injection (40) and that the DNA will be delivered intradermally, whereas the protein will be delivered intramuscularly.

2.9 Rationale for dose of Trimer 4571

The HIV-1 Env Trimer 4571 (VRC-HIVRGP096-00-VP) variant vaccine BG505 DS-SOSIP.664 consists of purified, formulated HIV-1 recombinant glycoprotein (gp140) as a soluble homotrimeric assembly of gp120-gp41 heterodimers, derived from the clade A HIV-1 strain BG505 and produced in a Chinese Hamster Ovary (CHO) DG44 cell line. Specifically, the BG505 DS-SOSIP.664 (Trimer 4571) possesses an engineered stabilizing disulfide bond between residues 201 and 433 (DS), maintaining the truncation at residue 664 in gp41, producing a soluble, cleaved Env trimer in a prefusion closed conformation. The ongoing and completed clinical trials with Trimer 4571 are listed in Table 2-2. Data on the safety and immunogenicity of Trimer 4571 + Alum from VRC 018 are available. No related SAEs were reported. The immunologic assays and analysis for this study are ongoing. Trimer 4571–specific Ab titers in serum samples were measured by electrochemiluminescence (ECLIA) using a Meso Scale Discovery (MSD) platform at baseline and at 2 weeks after the third product administration. Both the 100-mcg (n = 3) and 500-mcg (n = 5) doses elicited Trimer 4571– specific Abs, with geometric mean areas under the curve (AUCs) 8-fold and 40fold over background, respectively. No substantial difference was observed between the 100-mcg and the 500-mcg dose, so the 100-mcg dose will be tested in this trial.

For additional information, see the IB.

Table 2-2 Clinical trials with Trimer 4571

Protocol	Study status	N receiving Trimer 4571 + Alum	Route of administration and dose	Schedule	Safety data (clinicaltrials.gov)
VRC 018 / NCT03783130	Completed	16	IM or subcutaneous (SC) at 100 mcg or 500 mcg Trimer with 500 mcg Alum	0, 2, 5 months	As of August 2021, final study data: no related SAEs, related grade AEs, or related MAAEs were reported or other unexpected reactions, and no study pause criteria were met at any time. The clinical experience with Trimer 4571 will be updated in the IB Version 4.0 expected in September 2022
NIAID 19-I- 0069 / NCT03878121	Enrolling	Max 100	IM at 500 mcg Trimer with 500 mcg Alum	Boost post adenovirus vector prime	As of Jan 5, 2022, 12 participants have received study product. No SAEs, no SUSARs
NCT04985760	Enrolling	24	IM at 100 mcg or 500 mcg Trimer with 500 mcg Alum	0, 2 and 5 months	As of January 01, 2022, 5 participants have received either the 4571/alum or control. 2 participants have received two doses of study product and the remaining 3 have received a single dose. No related SAEs, no SUSARS

2.10 Rationale for dose of 3M-052-AF adjuvant

The 5-mcg dose of 3M-052-AF adjuvant has been selected based on preclinical data and clinical experience with other recombinant HIV envelope proteins in HVTN 137 and HVTN 300. The 500-mcg dose of Alum (ie, aluminum content by weight) adjuvant also matches the regimen in HVTN 137 and HVTN 300.

HVTN 137 has now completed enrollment in Part A and Part B. Based upon the available evidence, the HVTN 137 study team decided to proceed with a 5-mcg dose over a 1-mcg dose.

2.11 Rationale for FNA

To improve assessment of the effects of sD-NP-GT8 on B-cell lineage development, this protocol will employ FNA of an axillary lymph node proximal to the sites of vaccine administration. To assess the frequency of VRC01-class B cells from lymph nodes, FNA will be performed in a subset of participants in Groups 2 and 3 (at minimum 9 per group, half of each group). FNA will be performed approximately 3 weeks after both the second dose and the third dose of the sD-NP-GT8 immunogen. The germinal center response, which occurs exclusively in the lymphatic tissue, is critical for directing B-cell lineage development. Havenar-Daughton et al have employed repeated direct probing of germinal center responses by fine needle lymph node aspirates in NHP studies and found that the induction of nAbs against tier-2 autologous HIV strains best correlated with germinal center B-cell magnitude and Env-specific CD4+ Tfh cells (41). Similar sampling strategies are under evaluation in licensed vaccine and early-phase human HIV vaccine studies (42).

Fine needle aspirate of the axillary lymph node is a safe procedure with multiple studies reporting no significant complications with either FNA or core biopsy (a more invasive procedure than FNA) (43). The protocol team has developed eligibility requirements for the proposed procedures based upon guidelines from the American Society of Anesthesiologists, the American Board of Internal Medicine, the American Red Cross, the Society of Interventional Radiology, and a review of the scientific literature.

Specifically, it is a considered decision to include participants with obesity. The rate of obesity varies substantially by self-reported race with higher rates in populations identifying as Hispanic or non-Hispanic Black (44), and eligibility criteria related to obesity have been cited as a specific trial design barrier impeding the participation of women and underrepresented minorities (45). An extremely low rate of significant adverse events precludes identification of risk factors for poor outcomes, but we could find no evidence that Body Mass Index (BMI) is associated with increased complications with FNA. Additionally, diagnostic yields are higher in participants with obesity undergoing clinical FNA (46), an observation attributed to enhanced contrast between adipose and lymphatic tissue.

The team has also considered whether to include temporal limits on platelets/International Normalized Ratio (INR), and a temporal requirement to abstain from Non-steroidal anti-inflammatory drug (NSAID)/aspirin use prior to procedures. Routine measurement of INR has demonstrated no ability to identify patients who are at risk of periprocedural bleeding, even with higher risk procedures such as placement of central venous catheters (47). Additionally, platelets are assessed throughout the trial (including within 30 days of FNA). Hence the team has decided not to include INR measurement as a restriction. We also note that the trial eligibility criteria exclude persons with bleeding disorders (eg, factor deficiency, coagulopathy, or platelet disorder requiring special precautions [see Section 5.1.2]). Interventional radiology guidelines state that aspirin and/or NSAIDS are not a contraindication to FNA (48).

2.12 Rationale for leukapheresis

To assess the expansion of rare precursor B-cell populations that occur at a frequency of approximately 1 out of 20 million cells, a large number of peripheral blood mononuclear cells (PBMCs) is required. Leukapheresis can provide 6 to 10 billion PBMCs without depleting red blood cells or other blood components. There are approximately 1 million PBMCs per milliliter of blood; therefore, peripheral blood sampling at volumes associated with typical blood donation (~500 mL) would not provide sufficient PBMC numbers. Furthermore, leukapheresis is associated with fewer AEs when compared to blood donation. Hence, this protocol will employ leukapheresis in all study participants to ensure adequate specimens for analysis of rare precursors. Leukapheresis will be performed at screening and after the third dose of sD-NP-GT8 has been administered. The rationale for performing leukapheresis at 2 weeks after the third dose is based on previous studies that have assessed potentially rare VRC01-class memory B cells in the periphery (49).

Leukapheresis is a safe and well tolerated procedure with several studies reporting no significant late effects attributable to the procedure (50, 51). The protocol team has developed eligibility requirements for the proposed procedures (see Section 5.1) and leukapheresis eligibility criteria (see Section 8.6) as well as accounting for guidelines from the American Society for Apheresis, the American Society of Hematology, and review of the scientific literature.

The team has also considered whether to include temporal limits on platelets/INR, and a temporal requirement to abstain from NSAID/aspirin use prior to leukapheresis and has decided not to include these as restrictions (48). We note that the trial eligibility criteria exclude persons with bleeding disorders (eg, factor deficiency, coagulopathy, or platelet disorder requiring special precautions (see Section 5.1.2). Assessment of patients post leukapheresis found the most frequent side effect (39%) was paresthesia due to citrate-related hypocalcemia, managed with oral calcium supplements and/or slower rates. No bleeding occurred (52). The study team conclude that adverse reactions with leukapheresis are similar to those reported for conventional PBMC collections. Routine measurement of INR has demonstrated no ability to identify patients who are at risk of periprocedural bleeding even with higher risk procedures such as placement of central venous catheter (47).

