3.1 Primary objectives and endpoints

Objectives	Endpoints
1) To evaluate the safety and tolerability of 3 doses of sD-NP-GT8 + IL-12 DNA adjuvant with or without 2	 a) Local and systemic reactogenicity signs and symptoms will be collected for a minimum of 2 weeks following receipt of any study vaccine b) SAEs, medically attended adverse events (MAAEs), AESIs,
doses of Trimer 4571 + 3M- 052-AF/Alum adjuvant	and AEs leading to early participant withdrawal or permanent discontinuation will be collected throughout the study and for 12 months following any receipt of study products. Additionally, all AEs will be collected for 30 days after any receipt of study vaccination.
2) To evaluate the immunogenicity of 3 doses of sD-NP-GT8 + IL-12 DNA adjuvant with or	a) Response rate and magnitude of HIV-1–specific binding Ab responses to eOD-GT8-60mer, eOD-GT8 monomer, or Trimer 4571 as assessed by multiplex assay 2 weeks following the third (Groups 1 and 2) and fourth (Group 3) vaccinations
without 2 doses of Trimer 4571 + 3M-052-AF/Alum adjuvant	b) Response rate and magnitude of CD4+ and CD8+ T-cell responses, measured by flow cytometry, to HIV-1–specific Env peptide pools 2 weeks following the third (Groups 1 and 2) and fourth (Group 3) vaccinations
3) To evaluate the induction of VRC01-class B cells	a) Frequency of VRC01-class B cells from lymph nodes and periphery following the second and third vaccinations

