6.1.1 Power calculations for immunogenicity

The primary goal of the statistical immunogenicity analyses is to evaluate vaccine-induced immune responses in each treatment group by timepoint. The primary immunogenicity endpoints will be the response rate and magnitude of HIV-1–specific binding Ab responses, as measured by a multiplex assay; the response rate and magnitude of CD4+ and CD8+ T-cell responses to HIV-1– specific Env peptide pools, as measured by flow cytometry; and the frequency of VRC01-class B cells from lymph nodes and periphery following the second and third vaccinations, as measured by B-cell receptor (BCR) sequencing.

The primary and secondary statistical analyses of immunogenicity data will include the following comparisons:

- Group k postbaseline versus Group k at baseline to assess vaccine-induced immune responses within Group k, where k = 1, 2, 3. Groups 2 and 3 may be combined when comparing immune responses measured between baseline and Day 85 and those measured at baseline because participants in these 2 groups will have received the same products until Day 85.
- Group 1 versus Groups 2 and 3 combined to compare immune responses in the low- and high-dose groups (without administration of Trimer 4571) between Day 1 and Day 85.

- Group 1 versus Group 2 to compare immune responses in the low- and high-dose groups (without administration of Trimer 4571) post–Day 85.
- Group 2 versus Group 3 to compare immune responses with and without administration of Trimer 4571 post–Day 85.

[figure not shown]
Response magnitudes may be summarized using sample means and their two-sided 95% confidence intervals (CIs). Response rates will be estimated using empirical proportions; their two-sided 95% CIs will be constructed using the score method described in Agresti and Coull (1998) (53).

Comparisons of response magnitudes between timepoints within individual treatment groups or pooled treatment groups (eg, Groups 2 and 3 postbaseline versus baseline) will be carried out using Wilcoxon signed-rank tests.

Comparisons of response magnitudes between 2 independent groups (eg, Group 2 versus Group 3) within timepoints will be done using Wilcoxon rank-sum tests.

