The power achieved by the Wilcoxon rank-sum and the Wilcoxon signed-rank tests was computed as a function of the effect size for various sample sizes: n = 9, 15, 18, 30, 36, 45, including cases when no data are missing and cases when $\sim 17\%$ of the data are missing. These calculations also describe the power achieved by statistical comparisons of data measured in FNA samples if only 50% of participants enrolled in Groups 2 and 3 (ie, n = 9 participants per group or n = 18 in Groups 2 and 3 combined) consent to providing FNA samples. The calculations assumed that observations are normally distributed and that the number of observations in both groups or timepoints is identical.

The power function of the tests under these scenarios is presented in Figure 6-1. For instance, when comparing 2 independent groups of equal sizes n = 15 (eg. Groups 2 or 3 with about 17% loss to follow-up), the study achieves about 80% power to detect a significant difference at the 5% significance level using a twosided Wilcoxon rank-sum test if the average increase in the standardized (Cohen's) effect size is about 1.1. For example, if the proportion of VRC01-class B cells two weeks after the second vaccination was 1.0% in Group 1 and 2.1% in Group 2, with a standard deviation of about 1.0% in both groups, the standardized effect size would be 1.1 = (2.1%-1.0%)/1.0%, and the study would have approximately 80% to detect a significant difference between the two groups using a two-sided Wilcoxon rank-sum test at the 5% significance level. With a sample size of n = 18 per group (eg, Groups 2 or 3 with no loss to follow-up), the test has about 80% power to detect a significant difference if the standardized effect size is 1.0. Thus, if the proportion of VRC01-class B cells two weeks after the second vaccination was 1.0% in Group 1 and 2.0% in Group 2, with a standard deviation of about 1.0% in both groups, the standardized effect size would be 1.0 = (2.0%-1.0%)/1.0%, and the study would have approximately 80% to detect a significant difference between the two groups using a two-sided Wilcoxon rank-sum test at the 5% significance level.

[figure not shown]

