Appendix B Schedule of procedures: Participants not undergoing FNA

Visit	Number	01	02	03	04	05	06	07	08	09	10	11	12	AESI ¹⁶
	dy Week		0	2	4	6	7	12	14	15	24	26	52	78
	ly Month		0	0.5	1	1.5	1.75	3	3.5	3.75	6	6.5	12	18
S	tudy Day	-56 to 0	1	15	29	43	50	85	99	106	169	183	365	547
P	rocedure	Screen ¹	Vac 1		Vac 2			Vac 3			Vac 415			
Study procedures														
Assessment of Understanding		V												
Informed consent		V												
Medical history ²		V												
Physical exam ³		V	√	√	√	√		√	√		√	√	√	
Contraception status assessment ⁴		V	√		√			√			√			
Social impact assessment			√	√	√	√		√	√		√	√		
Social impact questionnaire					√			√					$\sqrt{}$	
Risk-reduction counseling ⁵		V	√	√	√	√		√	√		√	√	√	
Concomitant medications ⁶		V	√	√	√	√		√	√		√	√	√	
Adverse Events (AEs)			√	√	√	√		√	√		√	√		
AESIs/MAAEs/SAEs			√	√	√	√		√	√		√	√	√	V
Vaccination ⁷			√		√			√			√			
Reactogenicity assessment ⁸			√		√			√			√			
EP injection site assessment				√	√	√		√	√		√	√	$\sqrt{}$	$\sqrt{16}$
Clinical labs	Tube													
Pregnancy test (urine or serum) 9,10		V	√		√			√	√		√			
HBsAg/anti-HCV ¹⁰	SST	5												
HIV screening test, 10,11	SST	5												
Calcium ¹¹	SST	5												
CBC/Differential ¹⁰	EDTA	5		5		5			5			5		
ALT & Creatinine ¹⁰	SST	5		5		5			5			5		
HIV diagnostic test	EDTA							10				10	20	
Research samples ¹²														
PBMC for assays & storage	ACD			42.5		136		136 ¹³				136	178.5	
Serum for assays and storage	SST	34		34		34			34			34	34	
Leukapheresis ¹⁴		V							V					
Daily vol	ume (mL)	59	0	86.5	0	180		146	44		0	190	232.5	
56-day total vol	ume (mL)			145.5	145.5	325.5		326	370		0	190	232.5	

Green shading: Vaccination visit for all groups; Blue shading: Vaccination visit for Group 3 only; Gray shading: FNA visit not applicable to this subgroup.

- ¹ Screening evaluations at Visit 01 are performed no more than 56 days before Day 1.
- ² Medical history: A complete medical history is performed during screening. At enrollment and at subsequent visits, an interim medical history may be performed.
- ³ A complete **physical exam** is performed at screening and last clinic visit to include height, weight, and vital signs, and clinical assessments of head, ears, eyes, nose, and throat; neck and lymph nodes; heart; chest; abdomen; extremities; neurological function; and skin. At other visits, a **targeted physical exam** will be performed as needed, based on participant reports or indications of illness.

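### The peripheral VRC01-class endpoint after dose 2 rests on 136 mL of blood set against a leukapheresis baseline, and the plan neither reconciles this with Section 2.12 nor adjusts the paired test for unequal cell input

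*Protocol*

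**What the plan says.** Protocol Section 3.1 makes endpoint 3a primary: "Frequency of VRC01-class B cells from lymph nodes and periphery following the second and third vaccinations". Section 6.1.1 lists it again as a primary immunogenicity endpoint measured by BCR sequencing, and SAP Section 3.1 repeats it.

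Section 2.12 explains why leukapheresis is needed. The targets are "rare precursor B-cell populations that occur at a frequency of approximately 1 out of 20 million cells". Reckoning on about 1 million PBMC in each mL, the section concludes that "peripheral blood sampling at volumes associated with typical blood donation (~500 mL) would not provide sufficient PBMC numbers", and it puts the yield of a leukapheresis at 6 to 10 billion. Leukapheresis is scheduled at screening and two weeks after dose 3 (Visit 8), and at no time between.

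In Appendices A and B, the row "PBMC for assays & storage" shows 136 mL at Visit 5 (Day 43) and 136 mL at Visit 7 (Day 85, drawn before dose 3). Lymph-node aspiration after dose 2 is optional in Groups 2 and 3 and is not done in Group 1.

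Section 6.1.1 plans postbaseline-versus-baseline comparisons within groups by Wilcoxon signed-rank test, and the Figure 6-1 caption gives VRC01-class frequency as its example. The worked power example is a Group 1 v Group 2 comparison: "if the proportion of VRC01-class B cells two weeks after the second vaccination was 1.0% in Group 1 and 2.1% in Group 2".

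**The concern.** Section 2.12 sets a standard for how much blood is enough, and one primary measurement falls well short of it without explanation. The standard is not only about baseline: the section states the cell requirement for assessing expansion of the precursors, and applies leukapheresis after dose 3 as well.

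The shortfall also differs by timepoint. Baseline PBMC come from leukapheresis and post-dose-2 PBMC from a tube draw, so the two halves of the paired comparison can have very different cell inputs and detection limits. In someone with a small or absent response, a post-dose-2 zero may then reflect how few cells were examined. At stake is the within-group baseline contrast after dose 2, chiefly where responses are weak. In Group 1 blood is the only compartment sampled at that stage.

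**Working it through.** **1. Which samples exist.** The printed daily volumes confirm the PBMC source at each visit.
- Screening: 5 × 5 + 34 = 59 mL, as printed. No PBMC tube, so leukapheresis is the only baseline source.
- Visit 5: 5 + 5 + 136 + 34 = 180 mL, as printed. PBMC from 136 mL.
- Visit 7: 10 + 136 = 146 mL, as printed. A second 136 mL, eight weeks after dose 2.
- Visit 8: 5 + 5 + 34 = 44 mL, as printed. No PBMC tube; leukapheresis only.

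**2. Against Section 2.12's own standard.** At 1 million PBMC/mL, 500 mL gives 0.5 billion PBMC, against 6 to 10 billion by leukapheresis.
- One draw: 136/500 = 27%. Both draws pooled: 272/500 = 54%.
- Collection ratio: 6,000/136 = 44-fold to 10,000/136 = 74-fold.

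**3. Expected target cells.** λ = mL × PBMC/mL × share × 1/20,000,000, with Poisson CV = 1/√λ and no processing loss. Section 2.12 does not say whether its rate is per PBMC (share = 1) or per B cell. For the latter I assume that B cells are 5-15% of PBMC; that share is not in the documents.

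| Sample and reading | λ | CV |
|---|---|---|
| 136 mL, per PBMC, 1 million/mL | 6.8 | 38% |
| 136 mL, per PBMC, 2.0-3.3 million/mL | 13.6-22.7 | 27-21% |
| 136 mL, per B cell (5, 10, 15%), 1 million/mL | 0.34, 0.68, 1.02 | 171, 121, 99% |
| 500 mL, per PBMC, 1 million/mL | 25 | 20% |
| Leukapheresis, per PBMC | 300-500 | 5.8-4.5% |

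The second row is there because the protocol's inputs do not quite agree. Section 8.6 says about 3 L is processed, and 6 to 10 billion from 3 L implies 2.0 to 3.3 million PBMC/mL. On that density the collection ratio is 3,000/136 = 22-fold, while the 27% in step 2 is unchanged.

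Under the per-B-cell reading, the chance of seeing at least one target cell in 136 mL, 1 − exp(−λ), is 29%, 49% and 64%.

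**4. Effect of expansion.** With an assumed 10-fold rise, 6.8 becomes 68 cells and the CV falls to 12%.

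**5. Effect on the signed-rank test.** I simulated an unchanged true frequency, Poisson counts, 6 billion PBMC at baseline against 136 million after dose 2, and groups of 9 to 36.
- Per PBMC, the two-sided error stays at about 5%.
- Per B cell, at the assumed 5-15% share, it is roughly 5-15%, and nearly all the false positives are decreases. At λ = 0.68, for instance, exp(−0.68) = 51% of participants show zero and so fall below a non-zero baseline. The figure varies with group size and rises further if true frequencies vary widely between participants.

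**6. What restricting the primary periphery to Visit 8 would cost.** Section 6.1.1 allows Groups 2 and 3 to be combined against Group 1 only up to Day 85. Simulated rank-sum power at a standardized effect of 1.1 is about 79% for 9 v 36 and about 70% for 9 v 18, with full enrolment.

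**The case against.** The strongest reply is that the 1 in 20 million is a precursor frequency and vaccination is meant to raise it. That stands in part: the noise matters only for small or absent responses. But the same reply would apply after dose 3, where leukapheresis was still judged necessary, and the protocol does not say why 136 mL suffices after dose 2.

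Second, 6 to 10 billion is a collection yield, not an assay input. The laboratory may assay matched aliquots. Detail is left to the Central Assay Plan, which is not among these documents, and the SAP supplied is for safety. This also stands: unequal input is a possibility that the plan leaves open, not an established fact. It is a reason to state the input.

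Third, a reader might infer that the power example fails. The documents do not show that. Its percentages have no stated denominator, its standard deviation of about 1.0% may already include counting error, and its power depends only on the standardized effect and n. I reproduce the stated 80% or so (79.8% at 15 per group and effect 1.1; 80.3% at 18 and 1.0). Adding noise for 6.8 expected cells in Group 1 lowers the first only to 72%, and for 68 cells to 78%. Moving the example to Visit 8 would change no figure.

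Fourth, a reader might infer that Visit 5 should lose primary status. That would give up the pooled dose contrast and Group 1's only sampled compartment after dose 2. Appendix C already labels Visit 8 as the primary immunogenicity visit, but the label may refer to the antibody and T-cell endpoints.

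**Conclusion.** There is an unexplained inconsistency in a primary endpoint. The post-dose-2 peripheral measurement uses 27% of a volume that the protocol calls insufficient (54% with the Visit 7 draw), and the planned paired test takes no account of cell input that may differ by 22- to 74-fold from baseline. This does not show that the endpoint cannot be measured after dose 2.

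How much it matters depends on what the documents leave open. If the rate is per PBMC, expect about 7 to 23 target cells without expansion: noisy, but the test keeps its nominal error. If it is per B cell, at an assumed 5-15% of PBMC, expect 0.3 to 1.0 cells, and the test leans toward false decreases, which works against detecting weak induction. With marked expansion little remains of the problem. Cell losses in processing, not counted here, would make it worse.

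**What to change.** - In Section 3.1 (endpoint 3a), state that Visit 5 blood supplies the peripheral post-dose-2 measure.
- In Sections 6.1.1 and 6.4.2, require the number of B cells screened and the detection limit for each sample. Replace the unadjusted signed-rank comparison with baseline by one at matched cell input, or by a count model with cells screened as offset.
- Identify the Visit 8 leukapheresis as the adequately sized peripheral measurement, and reconcile Section 2.12 with endpoint 3a: say what 136 mL is expected to detect, and whether the 1 in 20 million is per PBMC or per B cell.
- Keep the Visit 5 contrast of Group 1 against pooled Groups 2 and 3, and leave the power example and the lymph-node endpoints as they are.

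No new procedure is needed. The cost is slightly more analysis work and, if inputs are matched by subsampling, some loss of baseline precision; the offset model avoids that loss.
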